- Change from baseline in number of binge days per week at Weeks 1, 2, 3, 4, 6, 8, and 10
- Change from baseline in number of binge episodes per week at Weeks 1, 2, 3, 4, 6, 8, 10, and 12
- Change from baseline in BE-CGI-S score at Weeks 2, 4, 6, 8, and 10
- Change from baseline in Y-BOCS-BE total score at Weeks 2, 4, 6, 8, and 10 and subscale scores (obsessions and compulsions) at Weeks 2, 4, 6, 8, 10, and 12
- Change from baseline in SDS total score and subscale scores (school/work disability, social life disability, and family life disability) at Weeks 6 and 12
- Change from baseline in MADRS total score at Week 12
- Change from baseline in HAM-A total score at Week 12
- Proportion of binge eating responders who have $\geq 75\%$ reduction in the number of binge eating episodes from Baseline at Week 12
- Change from baseline in EDE-Q modified including EDE-Q7 global score and 3 subscale scores (dietary restraint, shape/weight overvaluation, and body dissatisfaction) at Week 12

Safety Endpoints:

- The incidence of overall AEs, serious AEs (SAEs), and AEs (or SAEs) leading to discontinuations
- Clinical laboratory evaluations (serum chemistry, hematology, and urinalysis)
- Clinical evaluations (vital signs including orthostatic effects, and 12-lead ECGs)
- Frequency and severity of suicidal ideation and suicidal behavior as assessed by the C-SSRS
- Change and percent change from baseline in body weight at Weeks 1, 2, 3, 4, 6, 8, 10, and 12

- Change and percent change from baseline in BMI at Weeks 1, 2, 3, 4, 6, 8, 10, and 12
- Change from baseline in a fasting lipid panel (triglycerides, total cholesterol, high-density lipoprotein [HDL] cholesterol, and low-density lipoprotein [LDL] cholesterol) at Weeks 6 and 12
- Change from baseline in hemoglobin A1c level at Weeks 6 and 12
- Change from baseline in fasting glucose level at Weeks 6 and 12
- Change from baseline in insulin and high-sensitivity C-reactive protein (hs-CRP)
- Occurrence of symptoms of withdrawal from dasotraline measured by change from Week 12/EOT in:
 - CSSA total score at Weeks 13, 14, and 15
 - DESS total score at Weeks 13, 14, and 15
 - HAM-A total score at Weeks 13, 14, and 15
 - MADRS total score at Weeks 13, 14, and 15

Pharmacokinetic Endpoint:

Relationship between dasotraline plasma concentration and the primary endpoint in addition to selected secondary efficacy and safety endpoints

Statistical Methods:

Primary Efficacy Endpoint Analyses

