6.3. Other Secondary Efficacy Endpoints

The other secondary efficacy endpoints are:

- Change from baseline in number of binge days per week at Weeks 1, 2, 3, 4, 6, 8, and 10
- Change from baseline in number of binge episodes per week at Weeks 1, 2, 3, 4, 6, 8, 10, and 12
- Change from baseline in BE-CGI-S score at Weeks 2, 4, 6, 8, and 10
- Change from baseline in Y-BOCS-BE total score at Weeks 2, 4, 6, 8, and 10 and subscale scores (obsessions and compulsions) at Weeks 2, 4, 6, 8, 10, and 12
- Change from baseline in SDS total score and subscale scores (school/work disability, social life disability, and family life disability) at Weeks 6 and 12
- Change from baseline in MADRS total score at Week 12
- Change from baseline in HAM-A total score at Week 12
- Proportion of binge eating responders who have $\geq 75\%$ reduction in the number of binge eating episodes from Baseline at Week 12
- Change from baseline in EDE-Q modified including EDE-Q7 global score and 3 subscale scores (dietary restraint, shape/weight overvaluation, and body dissatisfaction) at Week 12

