11.3.7. Eating Disorder Examination Questionnaire (EDE-Q) Modified

Convergent findings from confirmatory factor analyses of item data from the EDE-Q obtained from patients with BED (Grilo-2010) and patients with overweight/obesity (Grilo-2012; Grilo-2013; Hrabosky-2008) as well as non-clinical groups (Grilo-2015) support an alternative, brief version of the EDE-Q and EDE comprising 7 items to generate a global score and 3 subscales (dietary restraint, shape/weight overvaluation, and body dissatisfaction) referred to as the EDE-Q7 (Grilo-2015). In the present study, the EDE-Q7 along with 3 items to assess binge eating, including the number of binge eating days will be used and referred to as the EDE-Q modified.

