15.4.1.5. Other Secondary Efficacy Endpoints Analyses

The other secondary endpoints are:

- Change from baseline in number of binge days per week at Weeks 1, 2, 3, 4, 6, 8, and 10
- Change from baseline in number of binge episodes per week at Weeks 1, 2, 3, 4, 6, 8, 10, and 12
- Change from baseline in BE-CGI-S score at Weeks 2, 4, 6, 8, and 10
- Change from baseline in Y-BOCS-BE total score at Weeks 2, 4, 6, 8, and 10 and subscale scores (obsessions and compulsions) at Weeks 2, 4, 6, 8, 10, and 12
- Change from baseline in MADRS total score at Week 12
- Change from baseline in HAM-A total score at Week 12
- Change from baseline in SDS total score and subscale scores (school/work disability, social life disability, and family life disability) at Weeks 6 and 12
- Proportion of binge eating responders (ie, $\geq 75\%$ reduction in the number of binge eating episodes) at Week 12
- Change from baseline in EDE-Q modified including EDE-Q7 global score and 3 subscale scores (dietary restraint, shape/weight overvaluation, and body dissatisfaction) at Week 12

Continuous variables (ie, change in number of binge days per week, number of binge episodes per week, BE-CGI-S, Y-BOCS-BE total score, and SDS total score and subscale scores) will be analyzed using an MMRM model similar to the primary efficacy analysis ([Section 15.4.1.2.1](#)) adjusting for the corresponding baseline. Other continuous variables (eg, change in EDE-Q7 global score and subscale scores) will be analyzed using an ANCOVA model similar to the supportive analysis for the primary efficacy endpoint ([Section 15.4.1.2.2](#)), adjusting for the corresponding baseline as a covariate.

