During the study and prior to database lock, the treatment assignments for all subjects are provided to the Bioanalytical Contract Research Organization (CRO) to facilitate plasma PK sample handling and analysis. No PK samples are analyzed for placebo subjects.

Protocol and IRT Amendment for Stratification Factor of Region

For this US study, there is no concern of ‘region’ difference for treatment effect. Sponsor’s initial intention of including stratification factor of region was to provide an optimization approach to ensure a balanced treatment assignment within each region. It should be noted that stratification by region was not implemented in study SEP360-221, which is also a US study with a similar study design.

The study team noticed on July 20, 2017 that the stratification by region was not implemented as planned, ie, the initiated sites in IRT were linked to incorrect regions (See [Section 6.1.5.1](#) for details). As of July 20, 2017, among 50 planned sites of this study, a total of 44 sites were screening subjects; and 137 subjects from 35 sites had already been randomized. Due to the ‘random’ nature of the incorrect assignment of region according to the root cause of this incident, the study team decided to remove stratification criteria related to ‘region’ to minimize the impact of this mistake. Stratification criteria were amended in study protocol V3.00 and randomization is to be balanced using only permuted blocks with baseline number of binge eating days per

321

week (3 – 4 binge eating days per week, > 4 binge eating days per week).

4. Changes in Planned Analyses

There is not any change made in this SAP from the analyses planned in the protocol.

5. Efficacy and Safety Variables

[Section 6.1.2](#) provides definitions of DB Baseline and Withdrawal Baseline. For the sake of simplicity, hereafter, Baseline and DB Baseline will be used in an interchangeable way.

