The Eating Disorder Examination Questionnaire (EDE-Q) is a self-report version of the eating disorder examination (EDE) (Fairburn-1994). Like the EDE, the EDE-Q measures eating-disorder psychopathology in the past 28 days and over longer intervals for diagnostic items. EDE-Q generates two types of data. First, it provides frequency data (ie, numerical data) on key behavioral features of eating disorders in term of number of episodes of the behavior and in some instance number of days which behavior has occurred; Second, they provide ratings (ie, categorical data), 4 subscale scores, and a EDE-Q global score reflecting the severity of aspects of the psychopathology of eating disorders. The 4 subscale scores are Restraint, Eating Concern, Shape Concern, and Weight Concern. Severity rating ranges 0- 6, where 0 represents absence of the feature and 6 represents an extreme degree. Frequency ratings range from 0 to 6 where 0='No days' or absence of the feature, 6='every day'.

Both of the Eating Disorder Examination Questionnaire Brief Version (EDE-Q7) and EDE-Q modified (EDE-QM) are brief versions of the EDE-Q. EDE-Q7 was used in study SEP360-221 while EDE-QM is used in this study (SEP360-321).

EDE-Q7 comprises 7 items to generate a global score and 3 subscale scores (Restraint, Shape Concern, and Weight Concern). The EDE-Q7 along with 3 items (see below) to assess binge eating, including the number of binge eating days, is referred to as the EDE-Q modified.

321

- **Item 4:** Over the past 28 days, how many **times** have you eaten what other people would regard as an **unusually large amount of food** (given the circumstances)?
- **Item 5:** On how many of these times did you have a sense of having lost control over your eating (at the time that you were eating)?
- **Item 6:** Over the past 28 days, on how many **DAYS** have such episodes of overeating occurred (i.e., you have eaten an unusually large amount of food **and** have had a sense of loss of control at the time)?

See [Table 1](#) below for definition of rating data for EDE-Q, EDE-Q7, EDE-Q modified, and their relationship. [Table 2](#) provides the definition of frequency data for EDE-Q, EDE-Q modified, and their mapping relationship.

Table 1: Rating Data of EDE-Q , EDE-Q7, and EDE-Q modified Items

EDE-Q Modified Item	EDE-Q7 Item	EDE-Q Item	Abbreviated Content	Subscale
1	1	1	Restraint over eating	Restraint
		2	Avoidance of eating	
2	2	3	Food avoidance	
3	3	4	Dietary Rules	
		5	Empty stomach	

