6.1.11.3 Composite Score

Unless otherwise specified, any individual missing item in any scale won’t be imputed. When calculating a total score, subscale score, composite score, or any assessment with more than one item (e.g. Y-BOCS-BE total score and 2 subscale scores, EDE-Q global score and 4 subscale scores, EDE-QM global score and 3 subscale scores, SDS total score and 3 subscale scores, MADRS total score, HAM-A total score, CSSA total score, DESS total score), if one or more items are missing at a visit, then the associated score (ie, total score or subscale score) will be set to missing.

In the event of missing data at Week 12 for efficacy variables, the last post-baseline observation carried forward (LOCF) approach is used to impute missing values in the ITT LOCF efficacy analyses. Unscheduled visits are included in the imputation.

For analyses of the change from baseline for a given efficacy parameter, only subjects who have both baseline and at least one post-baseline measurement are included.

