7.2.6.2 Analysis Methods

The analyses of continuous variables associated with the primary efficacy endpoint and the key secondary endpoints (ie, the change from baseline in number of binge days per week, BE-CGI-S score and Y-BOCS-BE total score) have been described on [Sections 7.2.3](#) and [7.2.4](#) of this SAP.

Continuous variables related to change in number of binge episodes per week, Y-BOCS-BE subscale scores, and SDS-total score and subscale scores will be analyzed using an MMRM model similar to the primary efficacy analysis ([Section 7.2.3.2.1](#)) with adjusting the corresponding baseline; other continuous variables with one scheduled post-baseline assessment (ie, change in MADRS total score, HAM-A total score, EDE-QM global score and subscale scores) will be analyzed using an ANCOVA model similar to the supportive analysis for the primary efficacy endpoint ([Section 7.2.3.2.3](#)) with adjusting the corresponding baseline as a covariate. The treatment differences and 95% CIs for each dasotraline group relative to placebo in the change from baseline will be obtained from this model.

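### SAP 5.1.4 gives the EDE-Q7/EDE-QM subscales as Restraint, Shape Concern and Weight Concern, which are not the subscale endpoints named in the protocol and SAP 7.2.6.1

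*SAP*

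**What the plan says.** The protocol is consistent about this instrument. Section 11.3.7 describes a seven-item short form with a global score and "3 subscales (dietary restraint, shape/weight overvaluation, and body dissatisfaction) referred to as the EDE-Q7". Section 6.3 lists the endpoint as "Change from baseline in EDE-Q modified including EDE-Q7 global score and 3 subscale scores (dietary restraint, shape/weight overvaluation, and body dissatisfaction) at Week 12", and the synopsis and Section 15.4.1.5 repeat the three names. SAP 7.2.6.1 does the same for the EDE-Q modified (EDE-QM): "3 subscale scores (dietary restraint, shape/weight overvaluation, and body dissatisfaction) at Week 12".

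SAP 5.1.4 differs: "EDE-Q7 comprises 7 items to generate a global score and 3 subscale scores (Restraint, Shape Concern, and Weight Concern". It then says that EDE-QM and EDE-Q7 subscale scores are equivalent, so this definition carries over to the EDE-QM, the version used in this study. Table 1 of that section, introduced as defining the rating data for all three versions of the questionnaire, assigns items to subscales. The text after Table 2 scores each subscale as the mean of its items and the global score as the mean of the subscales.

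The scores are then used. SAP 7.2.6.2 says that the "EDE-QM global score and subscale scores) will be analyzed using an ANCOVA model", with treatment differences and 95% confidence intervals. SAP Section 4 states: "There is not any change made in this SAP from the analyses planned in the protocol".

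**The concern.** The SAP defines two of the three subscales in two incompatible ways and gives scoring instructions for only one of them. A programmer who follows 5.1.4 will either leave two pre-specified other secondary endpoints unreported or report different scores under their names. If the conflict surfaces only after unblinding, choosing between the definitions becomes a post hoc decision. Because Section 4 declares no change, the Shape Concern and Weight Concern definition cannot be read as a deliberate, disclosed departure from the protocol.

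**Working it through.** The documents give no figure to reproduce. The check sets the definitions side by side and then applies the SAP's scoring rule.

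**Step 1. Items and subscales.** Each rating item runs from 0 to 6 (SAP 5.1.4). Table 1 gives the EDE-QM rating items as follows:

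| EDE-QM item | Content | Table 1 subscale |
|---|---|---|
| 1, 2, 3 | restraint items | Restraint |
| 8 | importance of shape | Shape Concern |
| 10 | dissatisfaction with shape | Shape Concern |
| 7 | importance of weight | Weight Concern |
| 9 | dissatisfaction with weight | Weight Concern |

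No short-form item falls under Eating Concern. The column therefore leaves exactly the three names that 5.1.4 gives the EDE-Q7, with 3, 2 and 2 items.

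**Step 2. Scores under SAP 5.1.4.** Write Qk for EDE-QM item k.

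- Shape Concern = (Q8 + Q10)/2
- Weight Concern = (Q7 + Q9)/2

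Each score covers only shape or only weight, and each mixes one importance item with one dissatisfaction item. By the labels, neither is a shape/weight overvaluation score, which should span both shape and weight.

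**Step 3. Scores under the endpoint names.** Neither document lists items for overvaluation or body dissatisfaction. The item labels suggest the following pairing, which is an assumption in everything below.

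- Overvaluation = (Q7 + Q8)/2
- Body dissatisfaction = (Q9 + Q10)/2

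**Step 4. Global score.** Both pairs sum to (Q7 + Q8 + Q9 + Q10)/2, so the mean of the three subscales is the same under either definition. Restraint (items 1–3) is also the same.

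**Step 5. How far the two subscales can differ.** Items 7–10 have 7⁴ = 2,401 complete response patterns.

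- Matching Shape with Overvaluation and Weight with Dissatisfaction gives a gap of |Q7 − Q10|/2 in each. The other matching gives |Q8 − Q9|/2. The better matching therefore leaves min(|Q7 − Q10|, |Q8 − Q9|)/2.
- The two pairs of values agree only if Q7 = Q10 or Q8 = Q9. They differ in 2,401 × (6/7)² = 1,764 patterns (73.5%) and agree in 2,401 − 1,764 = 637.
- A gap of at least 1 point needs both absolute differences to be 2 or more. Of the 49 pairs of item values, 49 − 7 − 12 = 30 qualify, so 30² = 900 patterns.
- The largest gap is 6/2 = 3.0 points, in 2² = 4 patterns.
- Example: items 7, 8, 9, 10 scored 2, 2, 6, 6 give Shape 4 and Weight 4, but overvaluation 2 and dissatisfaction 6.

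A full enumeration confirmed the 637 agreements, the 3.0 maximum and a global-score difference of 0.

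**Step 6. Effect on a treatment comparison.** Suppose treatment shifts both importance items by do and both dissatisfaction items by dd. Each SAP score then shows (do + dd)/2. With equal item SDs, correlation rw within a construct and rb across constructs, the SAP score's standardised effect relative to the larger endpoint effect is

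[(do + dd)/2] / max(do, dd) × √[(1 + rw)/(1 + rb)].

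The documents give no correlations, so these are assumed:

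| (rw, rb) | Square-root factor | One construct only (× 0.5) | Half effect on the other (× 0.75) | Equal effects (× 1) |
|---|---|---|---|---|
| (0.7, 0.6) | √(1.7/1.6) = 1.031 | 0.515 | 0.773 | 1.031 |
| (0.8, 0.4) | √(1.8/1.4) = 1.134 | 0.567 | 0.850 | 1.134 |
| (0.9, 0.3) | √(1.9/1.3) = 1.209 | 0.604 | 0.907 | 1.209 |

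The distortion can go in either direction.

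**The case against.** The strongest case is that this is a drafting slip of small consequence. Section 7.2.6.1 is the SAP's own endpoint definition and matches the protocol, so it governs what is reported. Table 1 cites a reference for the parent examination, and its subscale column may describe only the full EDE-Q. A programmer looking for the named outputs would find them missing from 5.1.4 and raise a query. These are two subscales within one of nine other secondary endpoints, outside the type I error strategy, and they can be recalculated from the items collected.

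Much of this stands. The impact is limited, and a slip is a plausible explanation. The pairing in Step 3 is inferred. The 73.5% weights all response patterns equally. The ratios in Step 6 rest on assumed correlations and equal item SDs, and they compare only with the larger effect. If one construct has no effect, the SAP score overstates that endpoint by showing half of the other's effect.

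The objection does not remove the conflict. The sentence in 5.1.4 gives the EDE-Q7 those subscale names explicitly, whatever Table 1's column was meant to cover. If the column is for the parent questionnaire only, the EDE-QM has no item-to-subscale map in the supplied text. The likelihood of a query is a reason to settle the matter in the SAP.

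**Conclusion.** The concern holds. The SAP contradicts itself and the protocol on two of the three EDE-QM subscales, and its only stated scoring rule produces scores that do not fit the endpoint names. Confidence in the conflict is high, because it rests on the wording of the two documents. Confidence in the 7+8 and 9+10 pairing is moderate, and every figure on the size of the difference depends on it.

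The consequence is that two pre-specified other secondary endpoints could be omitted or mis-scored. The conflict does not touch the global score, the restraint score, the primary and key secondary endpoints or the testing sequence, and no general loss of power is claimed. It should be corrected, but it does not threaten the trial's main conclusions.

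**What to change.** Before database lock:

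1. Give the EDE-Q7/EDE-QM its own subscale column in SAP Table 1, using the names in 7.2.6.1, with item lists taken from the instrument's scoring source. The expected lists are items 1–3 for dietary restraint, 7 and 8 for overvaluation, and 9 and 10 for body dissatisfaction. Confirm these against that source before the text is finalised.
2. Use the same three names in the 5.1.4 sentence that describes the EDE-Q7.
3. Keep Shape Concern and Weight Concern for the full EDE-Q collected at screening.

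If Shape Concern and Weight Concern are really intended for the EDE-QM, amend 7.2.6.1 instead and declare the change from the protocol in Section 4.

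The cost is a sentence, a table column and a scoring program, with no new data. One possible downside is that SAP 5.1.4 says Study SEP360-221 used the EDE-Q7 but not how its subscales were scored. A cross-study comparison of these two subscales may need them rescored.

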5.1.5. Sheehan Disability Scale (SDS)

The Sheehan Disability Scale (SDS) is to assess functional impairment in 3 domains: (1) work/school; (2) social life; and (3) home life. The subject rates the extent to which work/school, social life and home life have been impaired by his/her symptoms on a 10-point anchored visual analog scale (VAS). The subject’s responses for each domain are rated on the following scale: 0 = not at all; 1-3 = mildly; 4-6 = moderately; 7-9 =markedly; 10 = extremely. The 3 items can be combined into a single global measure of impairment (SDS total score) that ranges from 0 (unimpaired) to 30 (highly impaired). If any of the 3 SDS subscale scores is missing at a visit,

321

the SDS total score for that visit is also missing. A higher subscale score and total score are associated with greater illness severity.

The SDS is collected at Baseline, Weeks 6, and 12/EOT for randomized subjects, and at Week 15 for subjects who enter the withdrawal period.

5.1.6. Montgomery-Asberg Depression Rating Scale (MADRS)

The MADRS is a clinician-rated assessment of the subject's level of depression. This scale contains 10 items that measure apparent and reported sadness, inner tension, reduced sleep and appetite, difficulty concentrating, lassitude, inability to feel, and pessimistic and suicidal thoughts. Each item is scored in a range of 0 to 6, with higher scores indicating increased depressive symptoms. The score for each question will be summed to compute a total score ranging from 0 to 60. If the response to any question is missing, the total score will be missing.

The MADRS is collected at screening, Baseline and Week 12/EOT for randomized subjects, and at Weeks 13, 14 and 15 for subjects who enter the withdrawal period.

5.1.7. Hamilton Anxiety Rating Scale (HAM-A)

The HAM-A is a rating scale developed to quantify the severity of anxiety symptomatology. It consists of 14 items, each defined by a series of symptoms. The 14 items are: anxious mood, tension, fears, insomnia, intellectual, depressed mood, somatic (muscular), somatic (sensory), cardiovascular symptoms, respiratory symptoms, gastrointestinal symptoms, genitourinary symptoms, autonomic symptoms, and behavior at interview. Each item is rated on a 5-point scale, ranging from 0 (not present) to 4 (severe/disabling). The score for each question are summed to compute a total score ranging from 0 to 56. If the response to any question is missing, the total score is missing. A higher score is associated with a greater degree of anxiety. A score of ≥ 14 has been suggested to indicate clinically significant anxiety.

The HAM-A is collected at Baseline and Week 12/EOT for randomized subjects, and at Weeks 13, 14 and 15 for subjects who enter the withdrawal period.

